A total of 192 subjects diagnosed with DHS and who have met all necessary requirements for selection as subjects in the trial will be stratified into three balanced groups according to age, gender and VAS score in response to cold air stimulus at the time of baseline examination for final selection of subjects eligible to participate in the trial (64 per group). One of the three test products shall be randomly assigned to each of the three groups. The 0% and 15% nano-HAP-containing toothpastes and the 5% KNO₃ toothpaste shall be randomly coded as either A, B, or C by the manufacturer or Sponsor, and the code shall not be disclosed until all statistical analysis is complete.

Clinical Procedures

Immediately following the baseline sensitivity examination, each patient who qualifies to become a subject in the trial will be given and make the first use of his/her allotted test toothpaste, under the supervision of the Study Coordinator, after the latter has confirmed and recorded the weight of the tube. During the next 8 weeks, subjects will be required to brush their teeth twice daily with their allotted test product, as instructed, and not to take any food or drink for at least 30 minutes after brushing except for drinking water. A diary covering the duration of the study will be provided to each subject to (1) keep a record of number of times of brushing each day, and (2) record the name of any medication taken during the study period. All subjects will be asked to maintain their normal dietary habits. However, the use of oral hygiene products that are not related to this clinical trial, such as mouthwash and prescription medicine, along with dental clinic visits, dental treatment, professional plaque removal, whitening, use of pain relievers or commercial hypoallergenic products as well as use of narcotics, anti-inflammatory drugs, conventional analgesics, anticonvulsants, antihistamines, antidepressants, sedatives and other psychotropic drugs shall be prohibited throughout the course of the study.

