Alpha is the probability of rejecting a true null hypothesis.

Summary Statements

Group sample sizes of 38 in the first group and 38 in the second group achieve 80% power to detect non-inferiority using a one-sided, two-sample t-test. The margin of non-inferiority is 20%. The true ratio of the means at which the power is evaluated is 1.000. The significance level (alpha) of the test is 0.050. The COV of both groups are assumed to be 0.400.

With a sample size of at least 57 subjects per group completing the study, a non-inferiority test of means using two one-sided tests achieves 80% power at a 5% significance level for cold air stimulus sensitivity when the true ratio of the means is 1.000 and the non-inferiority limit of the mean ratio is 20%. Because the COV for tactile stimulus force is smaller, the study will have higher power for that outcome. To allow for 10% dropout, the study will enroll 64 subjects per group (192 subjects in total). Sample size calculations were performed using PASS 2019 (Kaysville, UT).

Dropout-Inflated Sample Size

Dropout Rate	Sample Size			Dropout-Inflated Enrollment sample size			Expected Number of Dropouts		
	N1	N2	N	N1'	N2'	N'	D1	D2	D
10%	38	38	76	43	43	86	5	5	10
10%	57	57	114	64	64	128	7	7	14

Definitions

Dropout Rate (DR) is the percentage of subjects who are expected to be lost at random during the course of the study and for whom no response data will be collected (i.e. who will be treated as "missing").

[figure not shown]
N1, N2, and N are the evaluable sample sizes at which power is computed. If N1 and N2 subjects are evaluated out of the N1' and N2' subjects that are enrolled in the study, the design will achieve the stated power.

N1', N2', and N' are the number of subjects that should be enrolled in the study in order to end up with N1, N2, and N evaluable subjects, based on the assumed dropout rate.

After solving for N1 and N2, N1' and N2' are calculated by inflating N1 and N2 using the formulas $N1' = N1 / (1 - DR)$ and $N2' = N2 / (1 - DR)$, with N1' and N2' always rounded up. (See references A7, pages 52-53, or A8, pages 32-33.)

D1, D2, and D are the expected number of dropouts. $D1 = N1' - N1$, $D2 = N2' - N2$, and $D = D1 + D2$.

Chart Section

Criteria for Test Aborting and Drop-out

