Subjects may withdraw from the trial at any time at their own request, or they may be withdrawn at any time at the discretion of the Principal Investigator or Sponsor for safety, behavioral, or administrative reasons. If a subject does not return for a scheduled visit, every effort should be made to contact the subject. In any circumstance, every effort shall be made to document subject outcome, if possible. The Principal Investigator should inquire about the reason for withdrawal, and request that the subject return all unused

test product, and return for a final visit, if applicable, and should also follow-up with the subject regarding any unresolved adverse events.

If a subject withdraws from the trial and also withdraws his/her consent for disclosure of future information, no further evaluations should be performed and no additional data should be collected. The Sponsor may retain and continue to use any data collected before such withdrawal of consent.

The Principal Investigator may discontinue a subject's participation if, in the opinion of the Principal Investigator, the subject is no longer a suitable candidate for the study. Possible reasons for such discontinuation include, but are not limited to:

- Adverse event
- Deviation from the protocol
- Missed appointment(s)
- Subject no longer meets eligibility criteria
- Use of antibiotic therapy or other prohibited medication during the study period

Criteria for Inclusion of Subjects as Appropriate for Efficacy Analysis

- Usage rate of toothpaste was 80% or more
- No evidence of events or activity likely to impair the reliability of the examination results, such as loss of diary records, etc.
- Subject has complied with the required restrictions during the examination period

Period of Data Storage :

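### Stopping the toothpaste is not separated from leaving the study, so week-8 cold-air scores can be lost for reasons related to response

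*Combined protocol and SAP*

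**What the plan says.** The section Criteria for Test Aborting and Drop-out gives a discretionary power: "The Principal Investigator may discontinue a subject's participation if, in the opinion of the Principal Investigator, the subject is no longer a suitable candidate". What ends is participation as a whole, not only use of the product. The list of reasons is open ("Possible reasons for such discontinuation include, but are not limited to"). It names adverse events, "Deviation from the protocol", missed visits, loss of eligibility, and "Use of antibiotic therapy or other prohibited medication during the study period". No threshold of severity or number is attached to any of them.

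Clinical Procedures sets the medication restrictions, which include "use of pain relievers or commercial hypoallergenic products as well as use of narcotics, anti-inflammatory drugs, conventional analgesics".

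For subjects who leave, the drop-out section asks for efforts to contact anyone who misses a visit, a best-effort record of the subject's outcome, and a final visit where that applies. It bars further evaluation only when a subject also withdraws consent for future information.

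The primary outcome (Efficacy outcomes, under Statistical Procedures) is the fall in cold-air VAS from baseline to 8 weeks. The visit schedule shows no early-termination visit and no retained week-8 visit for discontinued subjects. No method for missing data is given. The sample-size report defines dropouts as "subjects who are expected to be lost at random during the course of the study and for whom no response data will be collected".

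**The concern.** A subject without a week-8 cold-air score has no primary outcome. Several of the listed reasons could be related to how well the toothpaste works or is tolerated. In a pain trial, taking a pain reliever may reflect poor relief, and it is also prohibited medication. An adverse event may depend on the product. A subject who misses week 4 can be ended before the one visit that defines the primary outcome, although that subject might well have attended it.

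If poor responders leave an arm, the mean decrease among those who remain is too high. If this happens more in the nano-HAP arm than in the KNO3 arm, the ratio of means rises towards a false claim of non-inferiority. The 10% enrolment allowance restores the number of completers but does nothing about selection. A score never taken cannot be recovered at the analysis stage.

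**Working it through.** **Inputs from the plan.** COV 0.5 for cold air, ratio bound 0.80, one-sided alpha 0.05, 57 completers per group and 64 enrolled (Sample Size Calculation; Dropout-Inflated Sample Size). Non-inferiority is judged on the lower bound of a 95% CI (Data Analysis for Efficacy of the Primary Evaluation Item).

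**Assumptions not in the plan.** The true all-randomised ratio is 0.80. *m* is the share lost in an arm for outcome-related reasons. *r* is the lost subjects' mean decrease as a fraction of the completers' mean in the same arm. Completers keep a COV of 0.5, and 57 per arm are analysed.

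**Step 1: reproduce the plan's figure.** On the log scale, σ = √ln(1 + 0.5²) = 0.4724 and SE = 0.4724 × √(2/57) = 0.0885. The noncentrality is ln(1/0.80)/0.0885 = 0.2231/0.0885 = 2.52. With 112 df and one-sided 0.05, power is 0.80557, as printed. 57/0.9 = 63.3, rounded up to 64. The sample-size arithmetic is correct.

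**Step 2: ratio among completers.** An arm's full mean equals its completers' mean × [(1 − m) + m·r]. Hence:

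completer ratio = 0.80 × [(1 − m_KNO3) + m_KNO3·r] / [(1 − m_HAP) + m_HAP·r].

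**Step 3: chance of declaring non-inferiority.** This is a noncentral t with 112 df, one-sided 0.025 (the lower limit of a two-sided 95% CI) and noncentrality ln(completer ratio/0.80)/0.0885. For 10% loss in nano-HAP only:
- r = 0.5: 0.80/0.95 = 0.842; noncentrality 0.0513/0.0885 = 0.58; chance 8.3%.
- r = 0: 0.80/0.90 = 0.889; noncentrality 0.1054/0.0885 = 1.19; chance 21.8%.

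| Loss nano-HAP / KNO3 | r | Completer ratio | Chance of false non-inferiority |
|---|---|---|---|
| 10% / 0% | 0.5 | 0.842 | 8.3% |
| 10% / 0% | 0 | 0.889 | 21.8% |
| 5% / 0% | 0.5 | 0.821 | 4.7% |
| 5% / 0% | 0 | 0.842 | 8.3% |
| 10% / 7.5% | 0.5 | 0.811 | 3.5% |
| 10% / 7.5% | 0 | 0.822 | 4.9% |
| 10% / 10% | either | 0.800 | 2.5% |
| 0% / 10% | 0.5 | 0.760 | 0.6% |
| 0% / 10% | 0 | 0.720 | 0.1% |

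At the one-sided 0.05 used for the sample size, the first two rows become 14.3% and 32.2%, against a nominal 5%.

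**Check with a different parameterisation.** Take 7 of 64 lost from nano-HAP (64 − 57 = 7, so 10.9%) and measure the lost subjects' decrease against the whole arm's mean. The completer ratio is then 0.849 (half the mean) or 0.898 (no decrease), and the chances with the 95% CI are 9.8% and 25.4%. The size is similar.

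**The case against.** The case on the other side has force on several counts.

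- **The power is discretionary.** A reader might infer that one missed visit or one antibiotic course automatically ends participation and loses the outcome. The text says only that the investigator may do this, so outcomes can be lost but need not be.
- **The plan does not forbid later measurement.** A reader might infer that leaving always ends data collection. The drop-out section bars further evaluation only after consent for future information is withdrawn, and it asks for effort to contact absentees and to record outcomes. This stands. But permission is not a requirement, and an early final visit of unstated content does not supply a week-8 VAS.
- **Blinding limits selection by arm.** The pastes share a base formulation and are coded, so deliberate selection by arm is unlikely. Selection on outcome or tolerability remains possible, but it biases the ratio only if it differs between arms.
- **The efficacy criteria would drop many of these subjects anyway.** That set requires at least 80% usage and compliance with the restrictions. This is correct: collecting the score does not by itself remove the bias from the planned analysis. But no all-randomised analysis is possible without the score.
- **The random-loss wording is weak evidence.** It defines a term in a sample-size report and is not a rule for data collection.
- **Antibiotics.** A reader might infer a contradiction, because the prohibited list in Clinical Procedures does not name them. That same sentence mentions prescription medicine, in awkward syntax, so this is an ambiguity and not an established conflict.

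**Conclusion.** The point holds as a gap in what is collected. The drop-out section treats leaving the study as a single step, lists reasons that can be related to response, and does not tie later follow-up to the week-8 cold-air VAS. Followed as written, the plan can lose primary outcomes selectively.

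The size of any bias cannot be derived from the documents. The 8.3% and 21.8% are a stress case, with the full 10% allowance outcome-related and confined to the nano-HAP arm. A reader might take them as the expected error rate, but the documents give no support for one-sided loss. A modest imbalance (10% against 7.5%) gives 3.5% to 4.9%, equal loss with equal relative response leaves 2.5%, and loss confined to KNO3 lowers the rate. The figures show how sensitive the conclusion is; they do not forecast it.

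The change should be made before enrolment, because it is cheap and the missing scores cannot be recovered later.

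**What to change.** Leave decisions to discontinue, and the list of reasons, with the investigator as they are. Add to Criteria for Test Aborting and Drop-out:

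1. Stopping the test toothpaste is recorded separately from ending data collection.
2. Unless consent for further data is withdrawn, every randomised subject is asked to attend the already-scheduled 4- and 8-week cold-air and tactile examinations, with any deviation, medication or product-stop date recorded.
3. A missed week-4 visit does not by itself cancel the week-8 examination.

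In the statistical section, add an all-randomised analysis that uses the retained values, reported alongside the planned efficacy set. Without it, the efficacy criteria would still exclude many of these subjects.

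Separately, and as a clarification only, reconcile the antibiotic wording in the drop-out section with the prohibited list in Clinical Procedures.

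The cost is protocol wording plus attendance at visits already scheduled, for about 7 subjects per arm at the planned dropout rate. The small downside is that some week-8 values will come from subjects who are off product or using prohibited medication. These should be flagged in the data.

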Comparisons among the three groups for differences in the primary and secondary efficacy outcomes at each time point will be analyzed using analysis of covariance; because of the stratified randomization, age, gender, and baseline VAS cold air sensitivity will be included as covariates. Pre-planned post-hoc comparisons include: 1) pair-wise comparisons of the test product and the positive control against the placebo, to demonstrate effectiveness and 2) 95% confidence intervals (CI) for the ratio of means for the nano-HAP test product to the positive control to demonstrate non-inferiority of the test product with the positive control. Non-inferiority will be demonstrated if the lower

bound of the 95% CI falls within the 20% non-inferiority margin. If the data are log-normally distributed, then the analyses will be done on the log-transformed data. If the 95% CI for the difference between the test paste and the positive control is transformed back to the original scale, the back-transformed CI is a 95% CI for the ratio of means. If data are normally distributed, the 95% CI will be computed using Fieller's theorem, and the other condition that must be met to show non-inferiority is that the reference (i.e. positive control) mean must be significantly different from zero using a one-sided test. A 5% significance level will be used for all tests. From the results obtained for the placebo and positive control groups, it will be confirmed whether the non-inferiority margin used in the trial (20%) was appropriate or not.

(2) Data Analysis for the Efficacy of the Secondary Evaluation Item

Repeated measures analysis of covariance will be used for comparison between the 4-week and 8-week outcomes within each group. Interactions of the treatment effect with age, gender, and tactile sensitivity will be examined to evaluate significance of differential effects of the treatment by patient characteristics.

Sample Size Calculation

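### The only stated efficacy population is chosen on conduct after randomisation, so the comparisons with placebo have no all-randomised analysis

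*Combined protocol and SAP*

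**What the plan says.** The combined protocol and SAP describes the analysed population in one place, under the heading "Criteria for Inclusion of Subjects as Appropriate for Efficacy Analysis". It lists three criteria:

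- A threshold for product use, worded as "Usage rate of toothpaste was 80% or more".
- A condition on reliability with an open-ended list of examples, worded as "No evidence of events or activity likely to impair the reliability of the examination results, such as loss of diary records, etc".
- Adherence to the restrictions that the study places on subjects around the examinations.

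Each can be judged only once the treatment period is under way. Formally they are conditions for inclusion; a subject who fails one is left out.

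The section on data analysis for the primary evaluation item plans an analysis of covariance, the non-inferiority interval for the ratio of nano-HAP to KNO3, and "pair-wise comparisons of the test product and the positive control against the placebo, to demonstrate effectiveness". It gives none of these a population of its own. No intention-to-treat, full or all-randomised set is named anywhere, and no method is given for a missing 8-week VAS.

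Three other statements bear on the point:

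- The sample-size output defines dropouts as subjects "expected to be lost at random during the course of the study and for whom no response data will be collected". This is used only to inflate enrolment.
- Under the drop-out criteria, "In any circumstance, every effort shall be made to document subject outcome, if possible". The plan does not say how such data enter the analysis.
- Under randomisation, "the code shall not be disclosed until all statistical analysis is complete".

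**The concern.** Randomisation makes the arms comparable at baseline. Once subjects are removed for what they did on treatment, that protection holds only if removal is unrelated to outcome or acts alike in the arms being compared. A subject who gets no relief may brush less or take a prohibited pain reliever, so non-compliance can depend on response, and response may depend on the paste.

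For non-inferiority a compliant set is a usual and useful analysis, because non-compliance tends to make the arms look alike. For the superiority tests against placebo, which serve a stated study objective, the natural primary set is everyone randomised. Here the compliant set stands alone for both purposes. The placebo and KNO3 results will also be used to confirm that the 20% margin was appropriate, so selection could affect that check as well. Without an all-randomised result, a reader could not tell whether selection mattered.

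**Working it through.** **1. The plan's own figure.** Inputs from the Sample Size Calculation: COV 0.5, ratio bound 0.8, true ratio 1, one-sided alpha 0.05.

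- Log-scale SD = √ln(1 + 0.5²) = 0.4724
- Effect = −ln 0.8 = 0.2231
- Non-centrality at 57 per group = 0.2231 / (0.4724 × √(2/57)) = 2.522, with 112 df
- Power = 0.80557, as stated; 57/0.9 = 63.3, rounded up to 64, as stated

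The arithmetic is right. The 10% allowance covers only subjects with no response data. If a further 10% of the 57 failed the efficacy criteria, 51 per group would remain and power in this same calculation would be 0.766.

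**2. How far selection moves a mean.** The documents give no exclusion rates, so everything from here is assumed: 57 per arm before exclusion, normally distributed decreases, and a fraction f excluded.

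- *Wholly outcome-related*: probability 2f below the arm's own median, 0 above. The retained mean rises by 0.798 × f/(1−f) SD, where 0.798 = √(2/π).
- *Half outcome-related*: probability 0.5f for everyone plus f below the median. The rise is half as large.

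For f = 10% the rise is 0.0887 SD, and for f = 5% it is 0.0420 SD. An imbalance of 10% v 5% therefore shifts a comparison of two equal arms by 0.047 SD (wholly) or 0.023 SD (half).

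For the ratio, place nano-HAP on the margin (mean 0.8, KNO3 mean 1, COV 0.5, so SDs 0.4 and 0.5):

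- Wholly, 10% v 5%: (0.8 + 0.4 × 0.0887) / (1 + 0.5 × 0.0420) = 0.8355/1.0210 = 0.818
- Wholly, 5% v 10%: 0.8168/1.0443 = 0.782
- Half, 10% v 5%: 0.8177/1.0105 = 0.81

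**3. Error rates by simulation.** All tests are at nominal one-sided 2.5%, matching the 95% CI in the analysis section (the sample-size calculation uses one-sided 5%). Unadjusted runs used 200,000 trials per scenario: a Fieller contrast (nano-HAP mean − 0.8 × KNO3 mean) with Satterthwaite df, and a pooled t-test against placebo. Adjusted runs used 100,000 trials, with ANCOVA on baseline only and an assumed correlation of 0.3 or 0.6 between baseline and decrease.

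| Test | Excluded: tested arm v comparator | Wholly | Half |
|---|---|---|---|
| False non-inferiority, unadjusted | 10% v 5% | 4.2% | 3.3% |
| False non-inferiority, ANCOVA | 10% v 5% | 3.3–3.7% | 2.6–2.9% |
| False non-inferiority, unadjusted | 5% v 10% | 1.4% | 1.9% |
| False placebo win, unadjusted | 10% v 5% | 4.3% | 3.3% |
| False placebo win, ANCOVA | 10% v 5% | 3.9–4.3% | 3.1–3.2% |
| False placebo win, unadjusted | 5% v 10% | 1.4% | 1.8% |

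The reference for ANCOVA non-inferiority is 2.2% with equal exclusion, not 2.5%. The model pools the two unequal SDs, giving a contrast variance of 0.205 × 1.64 = 0.336 per subject against a true 0.16 + 0.64 × 0.25 = 0.32, so it is slightly conservative.

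**4. Equal exclusion (10% in both arms).**

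- Placebo test: no shift, 2.5%.
- Ratio test, equal COV: ratio 0.800, 2.4–2.5% unadjusted.
- Ratio test, common SD of 0.5: wholly (0.8 + 0.0443)/(1 + 0.0443) = 0.809 with 3.15–3.3% false non-inferiority; half 0.804 with 2.8%.

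Equal exclusion is therefore harmless to the ratio only under equal COV. The sample size assumes equal COV; an ANCOVA ordinarily assumes a common residual variance.

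**The case against.** The strongest reply is that a compliant set is standard for non-inferiority, the primary objective, and that this trial limits abuse of it. The pastes share a base formulation, the trial is double-blind, and the A/B/C code stays closed until analysis is complete. Usage can be checked against tube weights and diaries. The bias scenarios need exclusion that is both outcome-related and unequal, and the documents indicate neither. Wholly outcome-related exclusion is an extreme case. Under the planned covariate adjustment, the half-related non-inferiority result (2.6–2.9% against 2.2%) is close to nominal.

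Most of this stands as a limit on size. It does not supply an all-randomised analysis. A closed code restrains deliberate selection, but it cannot prevent bias when subjects who respond poorly are those who stop complying. Nor does the non-inferiority argument carry over to superiority over placebo. That the compliant set applies to the placebo tests is an inference, since the analysis section names no population, but it is the only set the text offers.

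A reader might go further and infer that the plan favours nano-HAP, or that exclusions will be picked to suit the result. The documents do not support either: they fix neither the size nor the direction of any bias, and the reverse imbalance makes the tests conservative. Nor are the open-ended wording of the reliability criterion and the unstated missing-data method separate errors. They are missing detail.

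**Conclusion.** The point holds as a cheap improvement. A stated rule limits the efficacy analysis to subjects selected on conduct after randomisation, and nothing in the document restores the randomised comparison for nano-HAP or KNO3 against placebo. Keeping the compliant set for non-inferiority is sound; having no other set is the weakness.

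The size is unknown. A 10% v 5% imbalance with half to all of the exclusion outcome-related would raise a nominal 2.5% error to at most about 4.3%, and the opposite imbalance would lower it to about 1.4% unadjusted. These figures rest on assumed exclusion rates, normal outcomes, the stated COV of 0.5 for the ratio and an assumed baseline correlation. They show what could go undetected and do not predict what will happen.

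**What to change.** Define a full analysis set of all randomised subjects, analysed as randomised, and make it primary for nano-HAP and KNO3 versus placebo. Report non-inferiority in both this set and the existing compliant set, and look for consistent conclusions.

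As supporting detail:

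- State how a missing 8-week VAS enters the full set, for example through a mixed model using baseline and 4-week VAS, and note its missing-at-random assumption. Subjects lost before week 4 contribute baseline data only.
- Replace the open-ended reliability criterion with a closed list of reasons.
- Fix exclusions subject by subject before outcomes are analysed, while the code is closed.

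Cost: SAP wording and a further model run. Excluded completers should already have 8-week data. There are two real downsides. Non-compliers dilute the effect: if 10% of an active arm gained nothing, its difference from placebo would shrink by 10%. For discontinued subjects the result leans on a missing-data assumption that cannot be tested.
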